2.4 CONSIDERATIONS on STATISTICAL ANALYSIS

2.4.1 Adjustments for Covariates

ANCOVA will be performed on primary and secondary endpoints using treatment group as independent variables. Details are described in 2.1 and 2.2

2.4.2 Handling of Dropouts or Missing Data

Data which are not adopted as a result of data missing of each analysis item or data handling in accordance with this statistical analysis plan item will be excluded from the analysis target for the statistical test or estimation of the evaluation.

2.4.3 Interim Analysis and Early Discontinuation

Interim analysis will not be performed.

2.4.4 Multicenter Studies

Analyses for consideration of centers will not be performed.

2.4.5 Multiple Comparisons/Multiplicity

It does not adjust multiplicity.

2.4.6 Use of an Efficacy Subset of Subjects

Not applicable in this study.

2.4.7 Active-Control Studies Intended to Show Equivalence

This is not an active-control study intended to show equivalence.

2.4.8 Subgroup Analysis

Subgroup analysis will be performed in 2.2.

3 SAFETY EVALUATION

3.1 Treatment -Emergent Adverse Event

3.1.1 Brief Summary of Adverse Events

Analysis Set: Safety Analysis Set

Items: TEAE

Classification: Causal relationship with [Related, Not related]
treatment/control drug

Severity [Mild, Moderate, Severe]

Method: For the above analysis items, the following analyses of frequency distribution will be performed

(1) Brief Summary of TEAE (events, subject, percent)

- 1) All TEAEs
- 2) TEAEs by causality
- 3) All TEAEs by severity
- 4) TEAEs leading to discontinuation
- 5) Serious TEAEs
- 6) Serious TEAEs by causality
- 7) Serious TEAEs leading to study drug discontinuation
- 8) TEAEs leading to death

Incidence rates will be calculated as following on each analysis

[Number of Subjects]

- Frequency by Causality

In case of the analysis by causality, subjects with one or more adverse events within a level of MedDRA term is counted only once as related AE.

- Frequency by Severity

Subjects with one or more adverse events within a level of MedDRA term will be counted only once in that level using the most severe incident.

- Others

Subjects with one or more adverse events within a level of MedDRA term will be counted only once for that MedDRA term. The denominator when calculating the incidence of adverse events is the number of subjects of safety analysis set.

[Number of Events]

Number of events will be allowed multiple counts for the subject with one or more adverse events within a level of MedDRA term.

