10.1.6 Causality of adverse events

The causal relationship of each adverse event to the study drug or comparative drug shall be classified and defined as shown below.

Related	An adverse event that follows a temporal sequence (including clinical course after discontinuation), or an adverse event in which there is at least a reasonable
---------	--

	probability that a causal relationship to the study drug or comparative drug cannot be ruled out, although other factors such as underlying disease, complications, or concomitant drugs/treatment are also suspected.
Not related	An adverse event that does not follow a temporal sequence from administration of the study drug or comparative drug. Very likely due to other factors such as underlying disease, complications, or concomitant drugs/treatment.

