3.1.2 Display of TEAE

Analysis Set: Safety Analysis Set

Items: TEAE

Classification: Severity [Mild, Moderate, Severe]

Method: For the above analysis items, the following analysis will be performed for each treatment group. Analysis variables will be coded using the MedDRA dictionary and be summarized into SOC and PT. SOCs will be sorted in alphabetical order, then PTs will be sorted in frequency order.

- (1) All TEAEs by SOC and PT
- (2) All TEAEs by SOC
- (3) All TEAEs by PT
- (4) Drug-related TEAEs by SOC and PT
- (5) All TEAEs by severity by SOC and PT
- (6) Drug-related TEAEs by severity by SOC and PT
- (7) TEAEs leading to discontinuation by SOC and PT
- (8) Serious TEAEs by SOC and PT
- (9) Non-serious TEAEs by SOC and PT

Incidence rates will be calculated as following on each analysis.

[Number of Subjects]

- Frequency distribution (by SOC/PT, SOC, PT)

Within each summary, subjects with one or more adverse events within a level of SOC term is counted only once in that level. Similarly, subjects with one or more adverse events within a level of PT term is counted only once in that level. The denominator when calculating the incidence of adverse events is the number of subjects of safety analysis set.

- Frequency by Severity (by SOC/PT)

Subjects with one or more adverse events within a level of SOC/PT term is counted only once in that level using the most severe incident. The denominator when calculating the incidence of adverse events is the number of subjects of safety analysis set.

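### The by-causality subject-counting rule in SAP 3.1.1 omits the condition that at least one event is related, so as written it leaves the Not related category empty

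*SAP*

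**What the plan says.** SAP 3.1.1 is the overview table of treatment-emergent adverse events, showing events, subjects and percentages. Item 2) is TEAEs by causality and item 6) is serious TEAEs by causality. The classification line gives two categories, "Causal relationship with [Related, Not related", with the bracket closing there.

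The rule for counting subjects opens "In case of the analysis by causality" and continues: "subjects with one or more adverse events within a level of MedDRA term is counted only once as related AE". The next rule, for severity, says that a subject with one or more events "will be counted only once in that level using the most severe incident". Events have a separate rule: "Number of events will be allowed multiple counts for the subject with one or more adverse events within a level of MedDRA term".

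SAP 3.1.2 holds the tables by SOC and PT. Table (4) is "Drug-related TEAEs by SOC and PT" and table (6) splits drug-related events by severity. The frequency rule there reads "Within each summary, subjects with one or more adverse events within a level of SOC term is counted only once in that level". The severity tables again use the most severe event.

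Protocol 10.1.6 has causality classified for each event. The definition of Not related begins "An adverse event that does not follow a temporal sequence from administration of the study drug or comparative drug".

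**The concern.** The sentence turns any adverse event into a related one at subject level. It does not require that one of the events be related, and it does not say where to put a subject whose events were all judged Not related. A subject whose single event met the protocol's definition of Not related would still be counted as Related.

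If this were programmed as written, the Related rows of the overview table would repeat the all-TEAE and all-serious-TEAE rows in both arms, and the Not related rows would show no subjects. Protocol 13.0 assigns the analysis to a CRO independent of the sponsor, so the written SAP is the instruction that the programmers work from. In an open-label study where causality is a judgement recorded at the site, the subject-level rule should be explicit.

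**Working it through.** The documents state no adverse event incidence, so there is no figure of the plan's to reproduce. The check is to read the rules against each other and then apply them to a small example.

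**Rules side by side**

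| Rule | Trigger | How the subject is classified |
|---|---|---|
| 3.1.1 causality, subjects | one or more events | once, as related; no condition |
| 3.1.1 severity, subjects | one or more events | once, at the most severe event |
| 3.1.1 events | each event | multiple counts; nothing forced to related |
| 3.1.2 tables (4) and (6) | one or more events among the drug-related ones | once per level; most severe event in (6) |

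The severity rule is complete because it names the hierarchy that decides the category. The causality rule has the same count-once form but no hierarchy, only a fixed outcome. Nothing else in the SAP supplies the missing condition for items 2) and 6).

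**Made-up example.** Five subjects with events judged related (R) or not related (N): [N], [N, N], [R, N], [R], [none].

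- Subjects with any event: 4.
- Written rule: related = 4, not related = 4 − 4 = 0.
- Usual rule (related if any R): related = 2 (third and fourth subjects), not related = 4 − 2 = 2.
- Events under either rule: R = 1 + 1 = 2; N = 1 + 2 + 1 = 4.

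Under the written rule the table would show 4 related subjects with 2 related events, and 0 not-related subjects with 4 not-related events.

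**Illustration at the planned arm size.** Assumptions: all 120 randomized subjects per arm are dosed; 10%, 20% or 40% have any TEAE; and between 10% and 50% of those have at least one related TEAE (counts rounded to whole subjects).

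| Any TEAE | Related, written rule | Related, usual rule |
|---|---|---|
| 12/120 = 10.0% | 10.0% | 1/120 = 0.8% to 6/120 = 5.0% |
| 24/120 = 20.0% | 20.0% | 2/120 = 1.7% to 12/120 = 10.0% |
| 48/120 = 40.0% | 40.0% | 5/120 = 4.2% to 24/120 = 20.0% |

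These rates are not from the documents. The table shows how the rules behave; it does not estimate an error in this trial.

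**The case against.** The strongest reply is that nobody would program the sentence literally. A reading that always empties one of two prespecified categories cannot be what the authors meant. Beside the severity rule, the causality sentence is naturally read as a tie-break: a subject with both kinds of event is counted once, as related. This stands as an account of intent and is the main reason why the point is minor. It does not make the sentence correct, because the tie-break is not stated.

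A reader might go further and infer that drug-related incidence would equal all-TEAE incidence throughout the safety report, so that a between-arm difference in related events would be hidden. The documents do not support that:

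- The 3.1.2 tables (4) and (6) take in only drug-related events, so an unrelated event never enters. Their counting rules contain no instruction to classify a subject as related.
- Event counts are printed beside subject counts in 3.1.1 and follow their own rule.
- The TEAE listing in SAP 4 gives the relationship to study drug for each event.

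A literal Related count would therefore clash visibly with these outputs. Nor do the documents make related events a separate endpoint: Protocol 5.2.2.2 names adverse events, hypoglycemia and hospitalization, and 13.1.4 plans frequency tables only.

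**Conclusion.** Wrong as written, and minor. The rule states a condition and an outcome that together give an incorrect count; this is more than a missing detail. Its reach is the subject counts and percentages in SAP 3.1.1 items 2) and 6), in both arms. No size in percentage points can be claimed, because every adverse event rate used above is assumed. The error would also appear only if the sentence were programmed literally, against the section's own two categories. The conclusion rests on the wording of 3.1.1 and on the absence of any other rule that repairs it for those two items.

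**What to change.** Replace the causality sentence in SAP 3.1.1 with:

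> In the analysis by causality, a subject with at least one related event at the level being summarised is counted once as Related; a subject all of whose events at that level are not related is counted once as Not related.

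Apply it to 3.1.1 items 2) and 6) only. Tables (4) and (6) in 3.1.2 need no change: they have no Not related category and their own counting rules are sufficient.

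The cost is one sentence in the SAP. It requires no new data and no protocol amendment, and no other planned output changes.

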3.1.2 Display of TEAE

Analysis Set: Safety Analysis Set

Items: TEAE

Classification: Severity [Mild, Moderate, Severe]

Method: For the above analysis items, the following analysis will be performed for each treatment group. Analysis variables will be coded using the MedDRA dictionary and be summarized into SOC and PT. SOCs will be sorted in alphabetical order, then PTs will be sorted in frequency order.

- (1) All TEAEs by SOC and PT
- (2) All TEAEs by SOC
- (3) All TEAEs by PT
- (4) Drug-related TEAEs by SOC and PT
- (5) All TEAEs by severity by SOC and PT
- (6) Drug-related TEAEs by severity by SOC and PT
- (7) TEAEs leading to discontinuation by SOC and PT
- (8) Serious TEAEs by SOC and PT
- (9) Non-serious TEAEs by SOC and PT

Incidence rates will be calculated as following on each analysis.

[Number of Subjects]

- Frequency distribution (by SOC/PT, SOC, PT)

Within each summary, subjects with one or more adverse events within a level of SOC term is counted only once in that level. Similarly, subjects with one or more adverse events within a level of PT term is counted only once in that level. The denominator when calculating the incidence of adverse events is the number of subjects of safety analysis set.

- Frequency by Severity (by SOC/PT)

Subjects with one or more adverse events within a level of SOC/PT term is counted only once in that level using the most severe incident. The denominator when calculating the incidence of adverse events is the number of subjects of safety analysis set.

3.2 Frequency of Hypoglycemia

Analysis Set: Safety Analysis Set

Items: Hypoglycemia During Study [Yes, No]

Incidence of Hypoglycemia (times) [0, 1, 2, 3, 4, 5<= - <=Max]

Method: Incidence rates will be calculated as following on each analysis.

(1) Frequency distribution

3.3 Hospitalization related to type 2 diabetes mellitus

Analysis Set: Safety Analysis Set

Items: Hospitalization Related to Type 2 [Yes, No]

Diabetes Mellitus

Period (Days) [Min<= - <7, 7<= - < 14, 14<= - <=Max]

Frequency (Times) [1, 2, 3, 4, 5<= - <=Max]

Method: Incidence rates will be calculated as following on each analysis.

(1) Frequency distribution

For subjects who hospitalized for type 2 diabetes, duration and number of times will be counted. For subjects who remain hospitalized at the end of this study, duration will be calculated by using the last examination date.

4 LISTINGS

Analysis Set: All Randomized subjects

Items: Demographics [Subject No., Site Name, Treatment group, Medication name(control drug), Informed consent date, Age (years) , Sex, Height (cm) , Weight (kg) , BMI (kg / m2) , Smoking Classification, Drink alcohol , Date of DM onset, Medical history(YN), Concurrent Medical Conditions (YN)]

Protocol Deviation [Subject No., Site Name, Treatment group, Age(years) , Sex, Contents of Protocol Deviation]

Excluded from [Subject No., Treatment group, Age(years) , Sex, Reason for exclusion]

Efficacy [Subject No., Site Name, Treatment group, Age(years) , Sex, Medical history(YN), Reported term for the medical history, SOC name, PT Name]

Concurrent Medical Conditions	[Subject No., Site Name, Treatment group, Age(years) , Sex, Concurrent Medical Conditions (YN), Reported term for the concurrent medical conditions, SOC name, PT name]
Medication for Concurrent Condition	[Subject No., Site Name, Treatment group, Age(years) , Sex, Medication for concurrent Condition (YN), Number of daily doses of drugs, Total number of daily tablets]
Concomitant Medications	[Subject No., Site Name, Treatment group, Age(years) , Sex, Concomitant medication during study(YN), Trade name or Generic medication name, Drug code, Drug code(label), Preferred name, Total daily dose, Dose unit, Total daily dose (as needed), Route, Medication start date, Medication end date, Medication given to treat PTE/AE, Adverse event, Indication]
Basic Information Questionnaire	[Subject No., Site Name, Treatment group, Age(years) , Sex, Analysis visit, Result(No.1-14)]
DTR -QOL Questionnaire	[Subject No., Site Name, Treatment group, Age(years) , Sex, Analysis Visit, Total score (Factor 1-Factor 4), DTR-QOL total score, Each score]
DTSQ	[Subject No., Site Name, Treatment group, Age(years) , Sex, Analysis Visit, DTSQ total score, Each score]
Withdrawal	[Subject No., Site Name, Treatment group, Age(years) , Sex, Reason, Details of reason, Date of last dose , Experience an overdose(YN), PTE/AE During Study(YN), Concomitant Medication(YN)]
Treatment drug / Control drug	[Subject No., Site Name, Treatment group, Age(years) , Sex, Dose date, Dose time (first) , Dose time (second)]
Laboratory Test	[Subject No., Site Name, Treatment group, Age(years) , Sex, Analysis Visit, Sample date, Item, Result, Normal/Abnormal, Specimen abnormal]

Hospitalization	[Subject No., Site Name, Treatment group,
Related to Type 2	Age(years) , Sex, Date of hospitalization, Date of
Diabetes Mellitus	discharge]
TEAE	[Subject No., Treatment group, Age(years) , Sex, Adverse event (Verbatim) , SOC name, PT name , AE start date, AE end date, Intensity, Relationship to study drug , Action Concerning Study Drug, Date Dose Stopped, Date Dose Restarted, Outcome, Date of Death, Seriousness]
Serious TEAE	[Subject No., Site Name, Treatment group, Age(years), Sex, Adverse event (Verbatim) , SOC name, PT name , AE start date, AE end date, Intensity, Relationship to study drug , Action Concerning Study Drug, Date Dose Stopped, Date Dose Restarted, Outcome, Date of Death,]
Dose Dispensed	[Subject No., Site Name, Treatment group, Age(years) , Sex, Date of dispensed, Quantity of dispensed, Drug unused confirmed date, Quantity of unused]
Investigational Drug	[Subject No., Site Name, Treatment group,
Overdose	Age(years) , Sex, overdose start date, overdose end date, maximum daily amount taken, related to study proc./product packaging, nature of overdose, details of overdose, any untoward occurrences?, concomitant medication, procedure, prescribed dose amended, unknown, Other]
Method:	Lists described above will be created for randomized subjects

Significance level, Confidence coefficient

- Significance level of 5% (2-sided) will be used for analysis.
- Confidence coefficient of 95% (2-sided) will be used for all confidence intervals.

REVISION HISTORY

Version	Date	Author	Revised Content
1.0	2017.1.10	PPD	First Edition
2.0	2017.12.28	PPD	Revision base on revised protocol Ver.1.
